9.10.11. Comprehensive Physical Examination & Targeted Physical Examination	<del>A comprehensive physical examination</del> Physical examinations must be performed by a physician, physician assistant, or registered nurse practitioner. A comprehensive physical examination must be performed as indicated in Table 4 and as documented within the medical record. Table 4. If the investigator observes no symptoms that warrant further examination, the investigator may forego a more detailed physical examination, and the targeted physical examination may be considered complete.	Clarification added to ensure targeted physical exams are performed, as indicated in Table 4, and more detailed physical exams are conducted when needed.
9.10.13 Study Drug Administration	Refer to Section 9.4 and 9.11 for treatment compliance and detail in dose management.	Language added to guide sites to the treatment compliance and dose management sections.
9.10.16. Adverse Event Collection	AEs should be reported from the time of the first dose until the Week 112 (B) visit as indicated in Table 4. For patients who discontinue study drug early (prior to Week 100) and continue to be followed in the study, all AEs should be recorded for 12 weeks following the patient’s last dose of study drug. Beyond 12 weeks after the patient’s last dose, only those AEs that are relevant to the clinical condition including kidney disease, may have an impact on kidney function, or may impact the interpretation of safety or efficacy data must be recorded in the AE log within the EDC. Unscheduled phone visits may be used, as necessary, to ensure accurate collection of AEs of interest. AEs that are related to study procedures should be recorded in the AE log within the EDC independent of the patient’s study drug status or duration since the patient’s last dose of study drug.	Clarification on the duration of AE reporting. Extended AE reporting period from 30 days following the last dose to 12 weeks following the last dose of drug, due to the collection of endpoint data through that period.

[REDACTED]	[REDACTED]	[REDACTED]

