Section	Version 6	Rationale
11.2.1.1. Adverse Event	
All AEs that are observed or reported by the patient during the study (from <del>time of</del> administration of the first dose <del>at the Day 1 visit</del> until <del>the final visit</del> 30 days following administration of the last dose of study drug) as indicated in Table 4 must be reported, regardless of their relationship to study drug or their clinical significance. <del>For patients who discontinue study drug early, AEs should be reported through 30 days following the date of last dose of study drug.</del>
 
SAEs, if considered related to study drug, can be reported at any time during the study duration. In addition, as noted in Section 11.2.1.2, death, initiation of dialysis, or transplant should be reported through Week 112, on the appropriate eCRF.
	
Adjusted the AE reporting timeframe to continue from the time of first dose through 30 days following administration of the last dose, for all patients.
 
Clarified that related SAEs can be reported through Week 112 (approximated 12 weeks following last dose of IP).

11.2.1.2. Serious Adverse Event	
The investigator is responsible for reporting to Reata or designee all AEs and SAEs that are observed or reported by the patient during the study (from the time of administration of the first dose of study drug until the final visit indicated in Table 4, as appropriate), including events resulting from protocol-associated procedures as defined in relevant legislation, and regardless of their relationship to study drug or their clinical significance. For patients who discontinue study drug early, SAEs should be reported through 30 days following the date of last dose of study drug. <del>with the exception of SAEs, if considered related to study drug, should be reported at any time during the study. In addition, death, kidney transplant, or initiation of dialysis, or transplant which</del> should be reported through Week <del>104</del> 112, on the appropriate eCRF (see Section 11.7). The Sponsor may request additional information from the investigator to ensure the timely completion of accurate safety reports.
	
Updated visit number based on added Week 112 visit.

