
Section 9.10.16 Adverse Event Collection
	
Patients will be observed for general appearance, presence of illness or injury, or signs indicative of a concurrent illness as indicated in Table 4. Patients must be instructed to volunteer any information regarding AEs on or after the first dose of study drug or sites may query the patients with an open question regarding any AEs they may be experiencing (e.g. “How have you been feeling since your last visit?”). Any findings are to be documented. Patients must be asked if they have been hospitalized, had any accidents, used any new medications, or changed concomitant medication regimens (including prescription drugs, over-the-counter medications, vitamins, herbal products, and minerals). Responses must be documented in the source documents. AEs should be reported from the time of the first dose through 30 days after the last dose (or the End of Study visit, whichever is earlier).
	
Clarification on Adverse Event Collection

Section 9.10.17 Kidney Ultrasound
	
Kidney ultrasound (historical or an ultrasound performed at Screen A) may be used <del>at Screen A</del> to diagnose ADPKD and to assess for eligibility based on the Modified Pei-Ravine Criteria. Patients with prior diagnosis of ADPKD will not have a kidney ultrasound performed as part of the study, but must provide documentation of ADPKD diagnosis for eligibility.
	
Updated language

Section 9.10.22 Coagulation
	
Samples will be collected for the following coagulation assessments as indicated in Table 4: Prothrombin Time (PT), and International Normalized Ratio (INR).
	
PT and INR added to obtain complete liver function assessment

Section	Version 5	Rationale

Section 9.10.23 Lipid Panel
	
Samples will be collected for the following lipid assessments as indicated in Table 4: Total Cholesterol, Low-Density Lipoprotein (LDL), High-Density Lipoprotein (HDL), and Triglycerides.
	
Lipid Panel added to understand the baseline clinical condition in the population, as hyperlipidemia is common in CKD

Section 9.10.24 SARS-CoV-2 Antibody Testing
	
Samples will be collected for SARS-CoV-2 antibody testing as indicated in Table 4.
	
Added SARS-CoV-2 antibody testing to determine whether patients contract SARS-CoV-2 and remain asymptomatic, as SARS-CoV-2 infection can impact kidney function

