
Section 9.10.31 Pharmacokinetic (PK) Blood Samples
	
Patients who have discontinued study drug should not complete PK procedures.
	
Clarification

Section	Version 5	Rationale
Section 11.2.1.1 Adverse Event	All AEs that are observed or reported by the patient during the study (from the time of administration of the first dose at the Day 1 visit until the final visit indicated in Table 4) must be reported, regardless of their relationship to study drug or their significance. For patients who discontinue study drug early, AEs should be reported through 30 days following the date of last dose of study drug.	Clarification
Section 11.2.1.2 Serious Adverse Event	The investigator is responsible for reporting to Reata or designee all AEs and SAEs that are observed or reported by the patient during the study (from the time of the first dose of study drug until the final visit indicated in Table 4, as appropriate), including events resulting from protocol-associated procedures as defined in relevant legislation, and regardless of their relationship to study drug or their clinical significance. For patients who discontinue study drug early, SAEs should be reported through 30 days following the date of last dose of study drug, with the exception of death, kidney transplant, or initiation of dialysis, which should be reported through Week 104 (See Section 11.7). The sponsor may request additional information from the investigator to ensure the timely completion of accurate safety reports.	Clarification
Section 11.4 Assessment of Causality	For regulatory reporting purposes, an adverse event is considered to be related when the causality evaluation is either “Definitely Related, Probably Related, or Possibly Related.” An adverse even is considered to be not related when the causality evaluation is either “Unlikely Related or Not Related.”	Clarification
Section 11.6 Recording Adverse Events	All drug-related (possibly, probably, or definitely related, see Section 11.4) AEs and abnormal laboratory test results reported or observed during the study must be followed to resolution (either return to baseline, <del>or</del> within normal limits, or stabilization). All other AEs will be followed through the final visit indicated in Table 4, as appropriate.	Clarification

Section	Version 5	Rationale

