6.2. Data Presentation Conventions

Unless otherwise specified, descriptive statistics for continuous variables include the number of patients with data (N), mean, standard deviation (SD), standard error (SE), first quartile (Q1), median, third quartile (Q3), minimum, and maximum. The same number of decimal places as in the observed value are presented when reporting minimum and maximum; 1 more decimal place than in the observed value is presented when reporting mean and quartiles; and 2 more decimal places than in the observed value are presented when reporting SD or SE.

Categorical data are presented using frequency counts and percentages. All percentages are rounded to 1 decimal place, unless otherwise specified. Percentages equal to 100 are presented as 100% and no percentages are presented for zero frequencies. Where individual variable values are missing, summaries of categorical data are based on reduced denominators (i.e., the denominators include only patients with available data), and the number of missing values is presented. For summaries of AEs and concomitant medications, the percentages are based on the total number of patients in each treatment group.

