6.3. Analysis Populations

Table 3 lists the analysis populations in the study.

Table 3: ANALYSIS POPULATION DEFINITION

Analysis Population	Definition
ITT (Intent-to-Treat)	All enrolled patients categorized by their randomized treatment group (whether or not they received study drug).
Safety	All enrolled patients who received at least 1 dose of study drug. The safety population is used for evaluation of safety variables. Patients who received 1 dose of bardoxolone methyl will be classified in the bardoxolone methyl group. Patients who received at least 1 dose of placebo and no dose of bardoxolone methyl will be classified in the placebo group.

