9.1. Adverse Event Preferred Term and Body/Organ System Summary Tables

Treatment-emergent adverse events are summarized by treatment as defined by the safety analysis set. In addition to being summarized by treatment year, AEs are also summarized overall.

Treatment-emergent adverse events are events that either:

- Have a complete date of onset on or after the date of first dose and not more than 30 days after the date of the last dose of study drug, or
- Have no recorded date of onset with a stop date after the first dose of study drug, or
- Have no recorded date of onset and stop date.

General considerations for TEAE summaries are:

- Multiple events by PT and SOC are counted once only per patient for summaries of TEAE incidence.
- For summaries of TEAE incidence by severity, only the most severe event is counted per patient.
- For summaries of TEAE incidence by relationship, only the most strongly related event is counted per patient.
- A TEAE with a missing resolution date or incomplete date that is not identified as continuing is assumed to be continuing.
- For summaries of the number of TEAEs, all TEAEs are counted.

Off-treatment AEs (OTAEs) are events with a start date more than 30 days after last dose and not considered treatment emergent. Off-treatment AEs will be summarized separately.

Adverse Events are coded using MedDRA. In MedDRA, each verbatim term is mapped to a preferred term and high-level term (HLT), which is then mapped to a SOC.

The investigator grades the severity of the AEs as mild, moderate, or severe as defined in the study protocol. The investigator grades association or relatedness to the study medication according to criteria specified in Section 11.4 of the protocol.

As defined in the protocol, an SAE is an adverse event (occurring at any dose and regardless of causality) that:

- Results in death;
- Is life-threatening;
- Requires inpatient hospitalization or prolongation of existing hospitalization;
- Results in persistent or significant incapacity or substantial disruption of the ability to conduct normal life functions;
- Is a congenital anomaly or birth defect in an offspring of a patient taking study drug;
- Is an important medical event.

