9.1.2. Summaries of Adverse Events

Treatment-emergent adverse events and OTEAEs are summarized by treatment. For each treatment, SOC, and PT, the number and percentage of patients reporting an event is calculated. In summary tables, SOC is presented alphabetically and events within each SOC are presented by decreasing frequency count. Additionally, summary tables of events within PTs are presented by decreasing frequency count may be generated.

Summary tables (number and percentage of patients and events) of TEAEs (by SOC and PT) are provided by treatment as follows:

- All TEAEs
- All related TEAEs (definitely, probably, or possibly related)
- All TEAEs by severity
- All serious TEAEs (including deaths)
- All non-serious TEAEs
- All related serious TEAEs (including deaths)
- All TEAEs leading to permanent discontinuation of study drug
- All TEAEs leading to study drug interruption
- All TEAEs leading to dose de-escalation
- TEAEs by time to onset (≤ 12 weeks and > 12 weeks)
- TEAEs exhibited in $> 5\%$ of patients in either treatment group

Listings are provided showing:

- All AEs
- Deaths
- SAEs
- AEs leading to permanent discontinuation of study drug
- TEAEs leading to study drug interruption
- TEAEs leading to dose de-escalation

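### Off-treatment AE percentages divide by all dosed patients, although protocol versions 5 and 6 did not routinely collect AEs beyond 30 days after last dose, so the printed rates are understated

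*SAP*

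**What the plan says.** SAP 9.1 splits adverse events at 30 days after last dose. Later events form their own group: "Off-treatment AEs (OTAEs) are events with a start date more than 30 days after last dose and not considered treatment emergent". No upper limit is set, and these events are to be summarized separately.

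SAP 9.1.2 applies the same statistic to both groups: "For each treatment, SOC, and PT, the number and percentage of patients reporting an event is calculated". SAP 6.2 fixes the denominator: "For summaries of AEs and concomitant medications, the percentages are based on the total number of patients in each treatment group". SAP 9 uses the safety set throughout, defined in SAP 6.3 as "All enrolled patients who received at least 1 dose of study drug". No section narrows the OTAE denominator to patients who were followed, or had AEs collected, beyond Day 30.

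The protocol change logs record how long AEs were collected after last dose:

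- **Version 5**, Section 9.10.16: "AEs should be reported from the time of the first dose through 30 days after the last dose". Section 11.2.1.1 adds: "For patients who discontinue study drug early, AEs should be reported through 30 days following the date of last dose of study drug".
- **Version 6**, Section 11.2.1.1, gives as its rationale: "Adjusted the AE reporting timeframe to continue from the time of first dose through 30 days" after last dose, for all patients.
- **Version 7**, rationale for Section 9.10.16: "Extended AE reporting period from 30 days following the last dose to 12 weeks following the last dose of drug".

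**The concern.** Under versions 5 and 6 the usual end of AE reporting coincides with the start of the OTAE definition. A patient whose time beyond Day 30 fell under those versions contributes few or no ordinary OTAEs but still counts in the denominator. The table cannot distinguish such a patient from one who was followed, asked, and had no event.

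Safety and tolerability are part of the primary objective (SAP 3.1.1), and the OTAE summary goes into the study report. A low off-treatment percentage could be taken as a finding about safety after withdrawal when part of it reflects missing ascertainment. The SAP does allow for protocol version elsewhere: it treats Week 52 values from before version 6 separately (SAP 6.5.2) and adjusts exposure for the old withdrawal period (SAP 9.2). It makes no such provision for OTAEs.

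**Working it through.** The plan states no OTAE rate, so there is no figure to reproduce. The check compares the collection windows with the SAP's counting rule and then sizes the effect.

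**1. Collection after last dose, by version**

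| Version (document date) | AE collection after last dose | Source |
|---|---|---|
| 2 to 4 (from 4 Mar 2019) | Throughout study follow-up | Version 2 log, Section 11.6; no change in the version 3 and 4 logs |
| 5 (25 Feb 2021) | 30 days in 9.10.16, and for early stoppers in 8.5.1 and 11.2.1.1; for others 11.2.1.1 still ran to the final visit. Death, transplant and dialysis to Week 104 | Version 5 log |
| 6 (4 Feb 2022) | 30 days for all in 8.3.3 and 11.2.1.1. Related SAEs at any time; death, dialysis and transplant to Week 112. Sections 11.2.1.2 and 11.6 still ran to the final visit | Version 6 log; the 11.6 text appears as a deletion in the version 7 log |
| 7 (25 May 2022) | To Week 112 (B). Early stoppers: all AEs for 12 weeks, then selected AEs only | Protocol 9.10.16, 11.2.1.1 |

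From the version 5 date to the version 7 date is 454 days, or 454/30.4 = 14.9 months (the SAP's own month length). These are document dates, not site adoption dates.

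**2. How much OTAE time is affected**

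- Version 6 completer, last visit at Day 85 to 92 after last dose: 85 - 30 = 55 to 92 - 30 = 62 days lie beyond Day 30. That is 55/85 = 65% to 62/92 = 67% of off-treatment follow-up, and the 30-day rule covers none of it.
- Version 5 completer, Week 104 visits at Day 28 to 36: at most 36 - 30 = 6 days. Under version 4 (Day 21 to 35): at most 5 days. Here follow-up ended; collection was not switched off. The patient stays in the denominator either way.
- Version 5 or 6 early stopper: visits could continue for many months, with no routine AE collection after Day 30.

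**3. Effect on the printed rate**

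Let N be the patients in the arm, p the true OTAE incidence, and f the share without collection beyond Day 30. Assume p is the same in both parts of the arm and that nothing is recorded in the unascertained part.

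Events recorded = N(1-f)p. Printed rate = N(1-f)p / N = p(1-f).

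| True p | f = 10% | f = 25% |
|---|---|---|
| 10% | 9.0% | 7.5% |
| 20% | 18.0% | 15.0% |
| 30% | 27.0% | 22.5% |

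The relative understatement equals f. Dividing by N(1-f) instead returns p. Both p and f are assumptions.

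If a fraction r of events in the unascertained part was recorded anyway, the printed rate is p(1 - f(1-r)). For p = 20%, f = 25% and an assumed r = 50%: 20% x (1 - 0.125) = 17.5%. The error shrinks but stays downward.

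**4. Between arms**

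With the same f in both arms, the ratio of printed rates equals the true ratio, and the difference shrinks by the factor (1-f). The comparison is tilted toward one arm only if f differs, which requires stopping times to differ by arm.

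**The case against.** The strongest reply has four parts.

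**The older texts were not uniform.** In both version 5 and version 6, at least one section still ran AE reporting to the final visit, so some sites may have recorded later events. This stands. A reader might infer that no ordinary OTAE could be recorded under those versions; the documents do not support that. They support saying that such events were not routinely collected. Mixed ascertainment is still no basis for one pooled percentage.

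**Collection beyond 30 days did not begin with version 7.** Versions 2 to 4 ran it throughout follow-up, so early stoppers under them were validly ascertained. This also stands. Restricting the table to version 7 patients would discard good data.

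**The size cannot be derived.** A reader might estimate f from dates. Assume uniform enrolment from mid-May 2019 to 10 May 2023 (1,456 days) and 700 days of dosing for everyone. The share of completers whose whole Day 31 to 84 period preceded version 7 is then 323/1,456 = 22%; requiring only Day 31 to precede it gives 376/1,456 = 26%. Neither figure is supported. The documents give no accrual data, the target rose from 300 to 550 to 850, not everyone completes, and amendments take effect only after ethics approval (Protocol 15.5). Patients still on drug at the 10 May 2023 notice stopped after the version 7 date, which also limits f.

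**The consequence is modest.** Safety summaries are descriptive, OTAEs are kept apart from treatment-emergent events, and all AEs, SAEs and deaths are listed. The SAP plans no on- versus off-treatment contrast. This is fair and keeps the point to a reporting correction; it does not make the percentage right.

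**Conclusion.** The point holds. Followed as written, the SAP prints OTAE percentages that can only be too low, because the denominator includes patients for whom events beyond Day 30 were not routinely collected or who had left follow-up. The relative understatement is f if nothing was recorded in those patients, and less if some events were. The documents do not give f; 10% to 25% is illustrative.

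What is distorted is the absolute off-treatment rate in each arm, and any reading of it against the on-treatment rate. A reader might infer bias in the treatment comparison; that would need stopping times to differ by arm, and the documents do not show that they do. The conclusion also assumes that collection broadly followed the stated windows. The change logs are used here as evidence of how the data were gathered, not as a conflict with current text.

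**What to change.** In SAP 9.1 and 9.1.2, do one of the following:

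- Base OTAE percentages on patients still in follow-up beyond Day 30 after last dose under a protocol version with AE collection open at that time: early stoppers under versions 2 to 4, and patients under version 7. Derive the flag from consent version and last-dose date, not from document dates.
- Report OTAEs per ascertained off-treatment person-time. This suits patients who changed version during off-treatment follow-up. For version 7 early stoppers, count time to 12 weeks, since only selected events are collected after that.

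With either choice, footnote the collection windows by version, list OTAEs from all other patients, and show deaths, dialysis and transplant for all patients, since those were captured throughout. State the number in the OTAE denominator for each arm, so that f becomes visible.

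The cost is SAP wording, one derived flag and a smaller denominator. No new data are needed.

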9.1.1. Missing and Partial Adverse Event Onset Dates

Rules for handling partial AE Onset Dates are included in Section 6.6.3.

9.1.2. Summaries of Adverse Events

Treatment-emergent adverse events and OTEAEs are summarized by treatment. For each treatment, SOC, and PT, the number and percentage of patients reporting an event is calculated. In summary tables, SOC is presented alphabetically and events within each SOC are presented by decreasing frequency count. Additionally, summary tables of events within PTs are presented by decreasing frequency count may be generated.

Summary tables (number and percentage of patients and events) of TEAEs (by SOC and PT) are provided by treatment as follows:

- All TEAEs
- All related TEAEs (definitely, probably, or possibly related)
- All TEAEs by severity
- All serious TEAEs (including deaths)
- All non-serious TEAEs
- All related serious TEAEs (including deaths)
- All TEAEs leading to permanent discontinuation of study drug
- All TEAEs leading to study drug interruption
- All TEAEs leading to dose de-escalation
- TEAEs by time to onset (≤ 12 weeks and > 12 weeks)
- TEAEs exhibited in $> 5\%$ of patients in either treatment group

Listings are provided showing:

- All AEs
- Deaths
- SAEs
- AEs leading to permanent discontinuation of study drug
- TEAEs leading to study drug interruption
- TEAEs leading to dose de-escalation

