#### **5.1.2.1. Fluid Overload**

Similar to endothelin receptor antagonists (ERAs) in certain patient populations, including bosentan in advanced congestive heart failure and avosentan in advanced CKD, bardoxolone methyl treatment was found to be associated with an increased risk for fluid overload and heart failure hospitalizations in the BEACON trial, which enrolled patients with Stage 4 CKD (eGFR 15 to 29 mL/min/1.73 m^2) and type 2 diabetes. The overall increased risk for fluid overload and heart failure events with bardoxolone methyl appeared to be limited to the first three to four weeks after initiation of treatment. Elevated BNP and prior hospitalization for heart failure were identified as risk factors that contributed to increased risk for these events. The increased risk for these events from bardoxolone methyl treatment had not been observed in six previous CKD studies, which were conducted mostly in patients with Stage 3b CKD (eGFR of 30 to 44 mL/min/1.73 m^2), patients with hepatic dysfunction, cancer patients, or healthy volunteers.

Review of admission notes and narrative descriptions for heart failure hospitalizations in BEACON indicates that heart failure in bardoxolone methyl-treated patients was often preceded by rapid fluid weight gain (several kilograms within the first weeks of treatment initiation) and was not associated with acute renal decompensation or acutely reduced left ventricular contractility. Available data from BEACON and other studies suggest that bardoxolone methyl treatment can differentially affect hemodynamic status according to the clinical condition of patients and likely promotes fluid retention in patients with more advanced renal dysfunction and other recognized risk factors associated with heart failure at baseline.

In a Phase 2 dose-ranging study of the efficacy and safety of bardoxolone methyl in patients with pulmonary hypertension (LARIAT), risk mitigation procedures were employed to reduce the potential for bardoxolone methyl-induced fluid overload; these procedures excluded patients with the identified risk factors and ensured close monitoring for fluid retention within the first month of treatment. To date, the risk for acute fluid overload AEs with bardoxolone methyl in late-stage CKD patients has not been observed in PH patients.

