#### **9.1.1. Management of Fluid Status**

Specific risk mitigation procedures will be employed to reduce the potential for bardoxolone methyl-induced fluid overload. These procedures include exclusion of patients with any severe renal disease, defined as an eGFR value of  $< 30 \text{ mL/min/1.73 m}^2$ . To exclude patients with significant cardiac dysfunction, the study will exclude patients with a history of left-sided heart disease. Patients who have evidence of volume overload at baseline, defined as BNP level of  $> 200 \text{ pg/mL}$ , will also be excluded.

Laboratory data and rapid weight gain will also be used to monitor fluid status after randomization. Patients who experience a BNP  $> 100 \text{ pg/mL}$  that represents a doubling (or more) of BNP levels from Day 1 should have an unscheduled telephone contact immediately to evaluate for any symptoms of fluid overload, and accordingly, request an unscheduled visit to assess signs and symptoms of congestive heart failure, heart failure, acute pulmonary edema, etc. identified through the telephone contact. In addition, patients will be given a Sponsor-provided scale to use at home to collect and record weights daily during the study. In the event the Sponsor-provided scale is temporarily unavailable (e.g., patient is traveling, replacement scale has not arrived to patient, etc.), patients may use any available scale. Use of a scale other than the Sponsor-provided scale should be documented in the patient diary. Patients who experience a weight increase of three pounds (1.4 kilograms) in a day or five pounds (2.3 kilograms) or greater increase within a week must have an unscheduled telephone contact immediately. Whether prompted by BNP elevations, sudden weight gain, or by the presence of clinical signs and symptoms the patient must be instructed to stop taking their study medication immediately and be medically evaluated by the investigator or a local physician within 1 to 2 days.

Investigators are encouraged to consider starting or increasing doses of diuretics (thiazides, loop diuretics) early after recognition of edema. This can be done concurrently with temporary discontinuation of the study drug. Patients may not restart their study medication until the investigator has completed and documented an assessment of fluid overload.

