Investigators should advise patients to watch for signs and symptoms of fluid overload. Patients should be informed to notify their physicians immediately if they experience swollen feet, chest pain, shortness of breath with mild exertion or while lying down, or other relevant symptoms. The investigator must immediately assess symptoms of fluid overload and determine appropriate medical management, as necessary, including whether stopping drug administration is required.

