Each AE should be recorded to represent a single diagnosis. Accompanying signs (including abnormal laboratory test values or ECG findings) or symptoms should NOT be recorded as additional AEs. If a diagnosis is unknown, sign(s) or symptom(s) should be recorded as an AE(s). Changes in laboratory test values or ECG parameters are only considered AEs if they are judged to be clinically significant (i.e., if some action or intervention is required or if the investigator judges the change to be beyond the range of normal physiological fluctuation). If abnormal laboratory test values or ECG findings are the result of pathology for which there is an overall diagnosis (e.g., increased creatinine levels in renal failure), only the diagnosis should be reported as an AE.

Elective procedures (surgeries or therapies) that were scheduled prior to the start of AE collection are not considered AEs. These elective procedures should not be recorded as AEs but should be documented in the patient’s source documents as elective (e.g., elective periodontal surgery). However, if a pre-planned procedure is performed early (e.g., as an emergency) because of a worsening of the preexisting condition, the worsening of the condition should be captured as an AE.

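### No visible adverse event table counts each patient once for fluid overload or heart failure, or isolates the first 4 weeks where the protocol places the earlier excess

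*SAP*

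**What the plan says.** SAP 9.1.2 lists eleven summary tables of treatment-emergent adverse events, all by system organ class (SOC) and preferred term (PT): "For each treatment, SOC, and PT, the number and percentage of patients reporting an event is calculated". SAP 9.1 gives the counting rule: "Multiple events by PT and SOC are counted once only per patient for summaries of TEAE incidence". High-level terms appear there only as a coding step; no listed table uses them. One of the eleven tables is "TEAEs by time to onset", with a single cut at 12 weeks. The other groupings over the treatment period are by treatment year and overall.

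Protocol 5.1.2.1 reports that the increased risk of fluid overload and heart failure in a previous Phase 3 trial in Stage 4 CKD with type 2 diabetes "appeared to be limited to the first three to four weeks after initiation of treatment". It adds that the increase "had not been observed in six previous CKD studies, which were conducted mostly in patients with Stage 3b CKD".

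Protocol 9.1.1 tells investigators to look for "signs and symptoms of congestive heart failure, heart failure, acute pulmonary edema, etc", and tells patients to report symptoms such as "swollen feet, chest pain, shortness of breath with mild exertion or while lying down". Under Protocol 11.6 each adverse event should be one diagnosis; when no diagnosis is known, the signs or symptoms are recorded instead.

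**The concern.** Fluid overload is a named risk of this drug, and one clinical condition can reach the database under several terms. A reader of the planned tables would want two facts: how many patients per arm had at least one such event, and how many of those first events fell in the period where the excess was seen before. The visible tables give neither. A PT row is too narrow. A SOC row counts a patient once, but mixes in every other term of that class and cannot join terms coded to different classes.

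Safety and tolerability is a primary objective (SAP 3.1.1), and still is in this SAP, which was written after clinical development was stopped. SAP 2 treats any analysis not specified before database lock as ad hoc and equates lock with unblinding. A term group assembled later would therefore be chosen with treatment known.

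**Working it through.** The plan states no figure on this point, so there is none to reproduce. The check has three steps.

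**1. Can the 12-week cell show the risk window?** Protocol 5.1.2.1 gives three to four weeks; Protocol 9.11.1 treats the first 8 weeks as the dose-escalation period. As shares of the 12-week cell:
- 3/12 = 25%
- 4/12 = 33%
- 8/12 = 67%

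A Week 2 event and a Week 11 event fall in the same row.

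**2. Can PT rows be turned into patients?** If rows hold r1, r2, ..., rk patients, the number of distinct patients lies between max(r) and the smaller of sum(r) and the arm size. As an assumed example, three rows of 4 give between 4 and 12 patients. That is 4/425 = 0.9% to 12/425 = 2.8% at the planned 425 per arm, or 4/300 = 1.3% to 12/300 = 4.0% at an assumed 300. This is a logical bound, not a forecast. The one-diagnosis rule in Protocol 11.6 makes heavy overlap between diagnosis rows unlikely, so for diagnoses the sum may be close to the truth. Overlap can still arise from symptoms recorded separately or from repeat events under different terms.

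**3. What would a 4-week row add?** All inputs here are assumptions: excess of 2.4 percentage points within 12 weeks, background 0.1% per week, 425 per arm. With q = background × weeks and p = q + excess in the window, the half-width is 1.96 × sqrt[p(1−p)/n + q(1−q)/n].

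For the 12-week cell, q = 1.2% and p = 3.6%, giving 15.3 versus 5.1 patients and a difference of 2.4 ± 2.05 points, whatever the onset pattern. Split at 4 weeks:

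| Onset of the excess | ≤4 weeks: patients; difference | >4 to 12 weeks: patients; difference |
|---|---|---|
| All in Weeks 1–4 | 11.9 vs 1.7; 2.4 ± 1.68 | 3.4 vs 3.4; 0 ± 1.20 |
| Even over 12 weeks | 5.1 vs 1.7; 0.8 ± 1.20 | 10.2 vs 3.4; 1.6 ± 1.68 |
| All after Week 4 | 1.7 vs 1.7; 0 ± 0.85 | 13.6 vs 3.4; 2.4 ± 1.88 |

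Three different patterns give the same 12-week cell; the two rows tell them apart descriptively. They need not be more precise: in the even case both rows include zero while the 12-week total does not. Over backgrounds of 0.02% to 0.3% per week, the 12-week half-width runs from 1.59 to 2.87 points at 425 per arm and from 1.90 to 3.42 at 300. With an excess of only 1.0 point (0.1% per week, 425 per arm) the 12-week difference is 1.0 ± 1.74. Hence the 12-week totals should stay.

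**The case against.** The strongest reply is that the plan already covers most of this.
- All adverse events and all serious events are listed, and onset dates are collected, so a count by patient and week can be recovered.
- Events leading to interruption have a table and a listing. Protocol 9.1.1 requires study drug to be stopped when BNP elevation, sudden weight gain or clinical signs raise suspicion, so these outputs are relevant.
- BNP and clinic weight are summarised at Weeks 1, 2, 4, 6, 8 and 12. BNP has shift tables, and BNP and NT-proBNP have patient-level thresholds.
- The monitoring committee reviews unblinded safety data during the trial.
- Development has stopped, the previous excess was in a different population, and this trial excludes eGFR below 30, BNP above 200 pg/mL and prior heart failure hospitalisation.

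All of this is correct and lowers the stakes. It does not supply the count. The interruption table and listing use single terms; the fluid overload reason in SAP 9.2 covers only interruptions judged not clinically significant; the BNP thresholds apply at any time in the study. A hand count from listings needs a term list, and the visible plan fixes none before unblinding.

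A reader might go further and infer that the plan has no grouped analysis at all. The documents do not support that, because Section 9.6 cannot be seen. Nor should one infer that finer week rows would separate the 20 mg and 30 mg steps: these fall at Weeks 4 and 6, the second only for ACR above 300 mg/g, and Protocol 9.11 allows slower titration.

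**Conclusion.** The point holds as a cheap improvement, limited to the visible SAP. It rests on two textual facts: no visible table counts each patient once for fluid overload or heart failure, and no visible row isolates the first 4 weeks. It does not rest on the assumed rates above, which only show how such a table would read.

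It is not an error in the design or in the efficacy analysis, and no data are lost. The documents do not show that an excess should be expected in this population. Nor could the added table show that the fluid-management measures worked, since both arms receive them; it would describe any difference from placebo.

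**What to change.** In SAP 9.1.2, before database lock and while blinded, fix a fluid overload / heart failure preferred-term list. Report by arm the number and percentage of patients with at least one such treatment-emergent event and with at least one such serious event, each patient counted once. Keep the ≤12 and >12 week totals, and inside the first show ≤4 weeks and >4 to 12 weeks from first dose, placing each patient at the first such event. Label the table descriptive, and state that the week rows do not separate the dose steps. If Section 9.6 already contains such a table, a cross-reference and the 4-week row are enough.

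The cost is SAP wording, one table and medical agreement on the list while blinded. No new data are needed. The rows are likely to hold few events.
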